2.5 Early study termination

A premature discontinuation will occur when a subject who signed the informed consent form (ICF) ceases participation in the study, regardless of circumstances, before the completion of all study assessments (i.e., before completing all protocol-stipulated activities). Subjects can be prematurely discontinued from therapy after careful consideration for any one of the following reasons:

- Screen failure
- Failure to receive complete critical pathway by not receiving dalbavancin in the post-period
- Withdrawal of consent (a clear reason will be documented)
- AE (before or after administration of first dose of antibiotic therapy)
- Protocol deviation/violation, including lack of protocol compliance
- Lost to follow-up (every effort will be made to contact the subject)
- Study or site prematurely terminated by the sponsor for any reason
- If a Gram-negative infection including bacteremia, an anaerobic infection, or fungemia develops during the study, or is subsequently found to have been present at baseline, the subject should be removed from study treatment and receive appropriate antibiotic(s) to treat the Gram-negative infection, anaerobic infection, or fungemia.
- Other reasons, such as specified administrative reasons or pregnancy

All subjects who prematurely discontinue from the study, regardless of cause, should have a final assessment at early termination (ET). A final assessment will be

^a If the patient is a woman of child-bearing potential, from at least the first dose of study drug until the final visit she must confirm strict abstinence from sexual intercourse with any male or must confirm use of an effective contraceptive method from the following list: A barrier (condoms, diaphragm or cervical cap) with spermicide; Oral or similar contraceptive, which includes, but is not limited to: injectable, implanted, or patch hormone therapy, and intrauterine device (IUD); Documented surgical sterilization at least 4 weeks prior to baseline; Partner vasectomy at least 6 months prior to baseline.

Within these limits, the specific form of contraception employed are left to the discretion of the patient, and/or the principal investigator, and/or the patient's physician.

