6.1 General Considerations

6.1.1 Analysis populations

Enrolled Set

The enrolled set consists of all patients who have signed informed consent and met all study eligibility criteria. Data will be summarized on disposition and baseline characteristics. Output will be summarized by study period (pre-period vs. post-period). All data listings will be reported for the enrolled set unless specified in Section 5.2.

Full Analysis Set

The full analysis set (FAS) population consists of all enrolled patients. Additionally, patients in the pre-period must receive at least one dose of antibiotics and patients in the post-period must receive at least one dose of dalbavancin for inclusion. All patients in the pre-period and post-period will be analysed. Data will be summarized by study period.

Data from all patients will be aggregated across sites, and all analyses related to protocol outcomes and baseline characteristics will be undertaken on the aggregate pre- and post-periods.

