6.1.5 Handling of missing and/or incomplete data

Patients will be missing specific data points for a variety of reasons. With the exception of validated instruments, missing values for a given time point will not be imputed and analyses will be conducted using an observed case approach. For validated instruments, missing items will be handled according to instructions from the relevant scoring manuals.

Where both date and time are collected, partial times (i.e. times with missing minutes or times with missing hours and minutes) will be estimated by a worst-case imputation approach (e.g., impute such that duration is the longest possible value). Analyses will be conducted using an observed case approach for partial or missing dates.

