6.2.6 Outcomes

6.2.6.1 Primary Outcomes

Primary Outcome: Hospital Admission Rate at Initial Episode of Care

Hospital admission at initial episode of care will include infection-related stays upon discharge from the index ED visit (derived and described in Appendix B). Tables will reflect patient counts and percentages for hospital admission (yes, no) at the initial episode of care by the pre-period and post-period for the FAS population. Summary rows will be repeated by site.

The primary analysis will consist of hypothesis testing using a one-sided, two-sample Pearson chi-square test for proportion difference with a normal approximation. An appropriate alternative method will be selected if a major violation to an assumption is present.

Because the baseline characteristics of the pre-period may differ from those of the post-period, a secondary analysis using a multivariate logistic regression analyses will be implemented. This model will assume mutual independence between the sites.

Clinically relevant baseline characteristics of interest for the adjusted analysis include the following variables: age, gender (Male, Female), race (White/Caucasian, Black or African American, Other), employment status (Full-Time, Part-Time, None), insurance plan type (Private commercial plan, Government funded, Uninsured, Other), Charlson Comorbidity Index, lesion surface area (<75cm², =>75 cm² – 150 cm², >150 cm²), infection type (Wound infection, Cellulitis/erysipelas, Abscess), prior health resource use (Yes, No, Unknown), prior antibiotic treatment failure (Yes, No, Unknown), presence of SIRS criteria (<2 or >=2), presence of recurrent infection in prior 6 months (Yes, No, Unknown), any health resource use in prior 3 months (Yes, No, Unknown), as well as is patient was immunocompromised (Yes, No, Unknown). Patients will be defined as immunocompromised if they have evidence of any of the following at baseline: Connective tissue disease, diabetes mellitus, leukemia, or malignant lymphoma. Categorical variables will be collapsed where possible. The primary predictor variable will be a pre/post-period indicator, and potentially other selected characteristics will be forced into the model based on clinical rationale and distributions observed in the

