7.0 List of Potential Tables/Listings/Figures

Table shells are included in the file 055123_ADVANCE_SAP_Table Shells_v 1.0_20181204.docx.

§ Denotes output that can be produced at interim analysis. f Denotes the minimum output necessary to support sample size confirmation. * Denotes output to be produced only for the sample size confirmation described in the protocol.

Table 1 Disposition of Study Patients by Site and All Patients: Enrolled Set§f
Table 2 Study Site Characteristics §
Table 3.1 Patient Demographics at Baseline by All Patients: Enrolled Set§
Table 3.2 Patient Demographics at Baseline by Site 10X: Full Analysis Set
Table 4 Comorbid Conditions Reported at Baseline: Full Analysis Set§
Table 5 Healthcare Resource Utilization at Previous 3 Months: Full Analysis Set§
Table 6 Infection characteristics and clinical characteristics during the initial assessment in the ED: Full Analysis Set§
Table 7.1 Care Pathways of Patients Following Initial Episode of Care: Full Analysis Set§
Table 9 Use of Antibiotics by Patients During the Study: Full Analysis Set§
Table 10 Primary Outcome: Hospital Admission Rate at Initial Episode of Care Full Analysis Set§f
Table 11 Primary Outcome: Primary Outcome: Hospital Admission Rate at Initial Episode of Care Multivariate Analysis Full Analysis Set§f
Table 12.1 Secondary Outcome: Total LOS during Initial Care and Follow-up: Full Analysis Set§f
Table 12.XX Secondary Outcome: Total LOS during Initial Care and Follow-up: Full Analysis Set: Site XXX§f
Table 13.1 Secondary Outcomes by All Patients: Full Analysis Set§
Table 13.2 Secondary Outcomes: Infection-related outpatient healthcare visits by Site 101: Full Analysis Set
Table 13.XX Secondary Outcomes: Infection-related outpatient healthcare visits by Site 10X: Full Analysis Set
Table 14 Secondary Outcome: Serious Adverse Events by SOC and PT: Full Analysis Set§
Table 15 Secondary Outcomes: Patient Satisfaction with Care: Full Analysis Set §
Table 16 Secondary Outcomes: Patient Work and Productivity Loss: Full Analysis Set§
Table 17 Secondary Outcomes: Patient Health-Related Quality of Life (SF-12): Full Analysis Set
Table 18 Other Outcomes: Full Analysis Set§
Table 19 Adverse Events- Overall Summary: Full Analysis Set§
Table 20 All Adverse Events by SOC and PT: Full Analysis Set§
Table 21 Adverse Events with Possible Causal Relationship to Study Drug by SOC and PT: Full Analysis Set§

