Appendix B: Derived Variables

Analysis Section (Visit)	Variable (Units)	Definition
General (Baseline)	Enrollment date	Informed consent date
General (Baseline)	Baseline date	Initial ED admission date
General (Initial Care)	Initial care indicator	If enrollment date \leq date \leq enrollment date + 13 days then = Yes Else = No
General (Follow-up)	Follow-up indicator	If enrollment date + 14 \leq date \leq enrollment date + 43 days then = Yes Else = No
Demographics (Baseline)	Age (years)	Round down to nearest integer((Initial ED admission date - date of birth + 1)/365.25), when both dates are available.
Demographics (Baseline)	BMI	weight (kg)/ [height(m)] ² Where necessary, height and weight will be converted to proper units.
Infection Characteristics (Baseline)	CCI	Will be scored as described in Appendix C. Includes variables for raw score and 10 year survival probability.
Infection Characteristics (Baseline)	Fever	If temperature > 38 ° C then =Yes Else =No
Infection Characteristics (Baseline)	Morbid Obesity	If baseline BMI \geq 40 then =Yes Else =No
Infection Characteristics (Baseline)	SIRS Criteria Met	SIRS criteria include abnormalities in temperature, heart rate, respiration, and white blood cell count. Specifically included are: 
 Fever of more than > 38.0°C or hypothermia with temperature < 36.0°C

[figure not shown]
[figure not shown]
Analysis Section (Visit)	Variable (Units)	Definition
		
 • Tachycardia with heart rate > 90 beats/minute or • Tachypnea with respiratory rate of > 20 breaths/minute or PaCO₂ of less than 32mmHg • Abnormal white blood cell count: leukocytosis >12,000/microliter, leucopenia <4,000/microliter, or >10% immature cells (bands).^{3,4} 
If 2 or more criteria present = Yes Else = No

Antibiotic Medications (Initial Care and Follow-up)	Days Received Antibiotic Medication	
Σ (Medication end date – Medication start date +1), when both dates are available. If dates overlap (e.g., end date and next start date are identical) then subtract 1 from summation for each occurrence.

Primary Outcome	Hospital Admission At Initial Episode of Care	
If discharge destination from the initial episode of care = Hospital and the reported hospitalization where discharge date = hospital date is infection-related then = Yes, Else = No

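### The set that carries the primary admission comparison keeps pre-period patients given any antibiotic but drops post-period patients not given dalbavancin, and no all-enrolled admission analysis is planned beside it

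*SAP*

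**What the plan says.** SAP 6.1.1 begins by stating that the FAS "population consists of all enrolled patients". It then adds a dosing condition for each period. Any antibiotic qualifies a pre-period patient, but "patients in the post-period must receive at least one dose of dalbavancin for inclusion". The Enrolled Set (consented and eligible) is used for disposition, baseline summaries and listings.

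SAP 6.2.6.1 tabulates "hospital admission (yes, no) at the initial episode of care by the pre-period and post-period for the FAS population". The table list in SAP 7.0 agrees: "Table 10 Primary Outcome: Hospital Admission Rate at Initial Episode of Care Full Analysis Set". Table 11, the multivariate version, is also FAS.

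Protocol 2.5 lists this among the reasons for premature discontinuation: "Failure to receive complete critical pathway by not receiving dalbavancin in the post-period". The same section says "All subjects who prematurely discontinue from the study, regardless of cause, should have a final assessment at early termination", so these patients are not meant to leave data collection unseen.

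Appendix B of the SAP codes the primary outcome as Yes under this condition: "If discharge destination from the initial episode of care = Hospital and the reported hospitalization where discharge date = hospital date is infection-related". Every other case is coded No. SAP 6.1.5 says that "missing values for a given time point will not be imputed and analyses will be conducted using an observed case approach".

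The primary objective (Protocol 1.3, SAP 2.1) is the difference in admission rate between patients receiving care before and after implementation of the pathway.

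**The concern.** Take two consented, eligible patients who are both given the same antibiotic, not dalbavancin. The pre-period patient is counted in the primary outcome and the post-period patient is removed. The selection occurs after enrolment (Appendix B dates enrolment at consent) and acts differently in the two periods.

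The study is not randomised. Its rationale (Protocol 2.1.2) relies on similar populations in the two periods, so matching entry rules matter. If the reason a post-period patient misses dalbavancin is also related to being admitted, the FAS post-period rate is no longer the rate among patients cared for after implementation. The one hypothesis test that the SAP does not label exploratory is run on this set.

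**Working it through.** **Is there another analysis that covers it?** In the visible text, no.
- Table 11 adjusts for baseline covariates but starts from the FAS, so it cannot restore dropped patients.
- The completers flag in Appendix B restricts the set further.
- SAP 6.2.1 reports enrolled and FAS counts, and Listing 8 shows hospital and ED records for the Enrolled Set. These would reveal how many were dropped, but neither is an analysis.
- The summary of dalbavancin use in SAP 6.2.5 is itself in the FAS, so it must show 100% in the post-period.

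**Inputs from the documents** (Protocol 5.3, SAP 6.1.2): 161 per period, one-sided 0.05, 38% versus 23%, at least 80% power.

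**Inputs assumed:** q, the share of enrolled post-period patients who do not receive dalbavancin; r, their admission rate. The documents give neither.

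**Step 1. Reproduce the plan's figure.** Pooled-variance normal approximation, with pooled rate 0.305:
- SE under the null = √(2 × 0.305 × 0.695 / 161) = 0.0513
- SE under the alternative = √((0.38 × 0.62 + 0.23 × 0.77) / 161) = 0.0506
- Power = Φ((0.15 − 1.645 × 0.0513) / 0.0506) = Φ(1.296) = 90.2%

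With 116 per period the power is 80.2%, so the stated figure of at least 80% holds and leaves room for attrition.

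**Step 2. Effect of the FAS rule when there is no true difference.** Let 38% of all enrolled patients be admitted in each period. Then

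FAS post-period rate = (0.38 − q·r) / (1 − q), spurious drop = q(r − 0.38) / (1 − q), post-period n = 161(1 − q).

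Example, q = 3%, r = 80%: (0.38 − 0.024) / 0.97 = 36.7%, a drop of 1.3 points. The rejection probability is Φ((0.0130 − 1.645 × 0.0543) / 0.0543) = 8.0%.

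| q | r | FAS post rate | Spurious drop (points) | One-sided error |
|---|---|---|---|---|
| 1% | 60% | 37.8% | 0.2 | 5.4% |
| 1% | 80% | 37.6% | 0.4 | 5.9% |
| 3% | 60% | 37.3% | 0.7 | 6.4% |
| 3% | 80% | 36.7% | 1.3 | 8.0% |
| any | 38% | 38.0% | 0 | 5.0% |
| 1% | 20% | 38.2% | −0.2 | 4.7% |
| 3% | 20% | 38.6% | −0.6 | 4.0% |
| 5% | 80% | 35.8% | 2.2 | 11% |
| 10% | 80% | 33.3% | 4.7 | 21% |

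One to three per cent of 161 is about 2 to 5 patients.

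**Step 3. Can an all-enrolled analysis go wrong?** Yes, through the Appendix B default. Suppose r = 80% and, as a worst case, every non-recipient's disposition is unrecorded and therefore coded No. The post-period rate becomes 0.38 − 0.8q: 37.2% at q = 1% and 35.6% at q = 3%. The error is 6.7% and 11.5%, worse than the FAS figures of 5.9% and 8.0%. Counting the same patients as admitted gives 0.38 − 0.8q + q, with error 4.6% and 4.0%.

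**Step 4. Dilution.** If recipients are admitted at 23% and non-recipients at 80%, the all-enrolled post-period rate is 0.23(1 − q) + 0.8q. Power at 161 per period, without attrition:

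| q | Post rate | Power |
|---|---|---|
| 0 | 23.0% | 90% |
| 1% | 23.6% | 88% |
| 3% | 24.7% | 83% |
| 5% | 25.9% | 76% |
| 10% | 28.7% | 55% |

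**The case against.** Each rule asks for one dose of that period's own treatment. Dalbavancin is part of the pathway's definition (Protocol 1.1.5), and Protocol 2.5 treats missing it as not receiving the complete pathway. A recipient comparison is therefore a coherent target, and the error rates above are errors only if the target is all patients cared for after implementation. This stands: which set is labelled primary is a choice of estimand. It does not remove the need for the other analysis, because the objective is worded in terms of implementation.

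Non-receipt is probably rare. All enrolled post-period patients are to receive the drug (Protocol 2.2.2), it is given at the point of care in the ED (2.1), sites are trained to obtain it (6.2), and consent covers the pathway (7.3). Patients unwilling to follow study procedures are excluded. This also stands, and it is why 1-3% is the range to weigh. Attrition above the assumed 10% (SAP 5.0) would shrink the test sizes slightly further.

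The absence of an all-enrolled analysis is judged from the visible text. The table list is headed as potential, the shells are in a separate file, and neighbouring sections are redacted.

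A reader might infer that the rule removes admitted patients from the post-period. It does not: dalbavancin recipients who are admitted stay in the FAS, and SAP 6.2.9 summarises why recipients were not discharged the same day.

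A reader might also infer that the test favours the pathway with an error of 11-21%. That needs 5-10% non-receipt with 80% admitted, and nothing in the documents supports either value.

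**Conclusion.** The point holds as a matter of design. The inclusion rule differs by period, acts after enrolment, and governs both the unadjusted and the adjusted primary analysis. No visible analysis shows whether the result depends on it.

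Its size is probably small and its direction is not known. On the assumed values (38% in both periods, 161 analysed per period), 1-3% non-receipt with 60-80% admitted moves the difference by 0.2-1.3 points against a planned 15, with one-sided error of 5.4-8.0%. At 38% admitted there is no bias, and below that it works against the pathway.

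The documents do not support calling the FAS result invalid, or requiring the sponsor to demote the FAS. They do support an added analysis that answers the objective as worded. The FAS definition also needs rewording however few patients are dropped, since its first sentence and its dosing conditions disagree.

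**What to change.** 1. Repeat the Table 10 and Table 11 admission analyses on the Enrolled Set, or on enrolled patients with at least one dose of any antibiotic in both periods. Report them beside the FAS result. Require any claim about implementing the pathway to be consistent across both. The sponsor chooses which set is labelled primary and says which question each one answers.
2. For this analysis, take the index ED disposition from the medical record for every enrolled patient, including those who did not receive dalbavancin. Apply the Appendix B default of No only when that disposition is known. Set unknown disposition to missing, in line with SAP 6.1.5, and add a sensitivity analysis that counts it as admitted. Without this step the added analysis could be worse than the FAS.
3. Reword SAP 6.1.1 so that the description of the FAS as all enrolled patients agrees with the dosing conditions.

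Cost: wording in SAP 6.1.1, 6.2.6.1 and Appendix B, a second version of two tables, and a completeness check on index disposition for what is probably a handful of patients. Listing 8 covers the Enrolled Set, but its title does not show that the records are complete. The statistical downside is dilution if non-recipients are often admitted: with 80% admitted, power is 88-83% at 1-3% non-receipt against 90% with full receipt, and it falls below the planned 80% if non-receipt reaches 5%.

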6.1.2 Sample size

Hospital admission rate, which is correlated to total hospital time for the study population, was largely unknown for purposes of sample size estimation. The final enrollment to support hypothesis testing for a primary outcome of total admitted hospital days was initially calculated as 322 subjects (161 subjects in each period). The sample size was evaluated after a planned interim analysis of pre-period data once 75 subjects were enrolled in the pre-period. Based on results of the interim analysis, an adjustment was made at the time of the analysis to revise the primary outcome from total admitted hospital days to hospital admission rate at initial episode of care. The initially estimated final enrollment of 322 subjects, including adjustments for attrition, would support one-sided hypothesis testing (two-sample Pearson chi-square test for proportion difference with equal group weights using a normal approximation) with a significance level of 0.05 and at least 80% power assuming hospital admission rate comparing the pre- and post-periods were 38% versus 23%.

6.1.3 Rounding

Means and medians will be rounded to one decimal more than that which the variable was recorded. Standard deviations will be rounded to two decimals more than that which the variable was recorded.

Percentages will be rounded to the nearest integer. Percentages for responses to a variable will only include patients with non-missing data, i.e. the denominator will be the number of patients with non-missing data.

P-values will be reported to three decimal places. Probabilities that are <0.001 will be presented as " <0.001 ."

6.1.4 Handling of outliers

Outliers will be examined using descriptive statistics, making sure that the minimum and maximum of the variable of interest are not unusually small or large and that the standard deviation seems appropriate for the data. If an outlier(s) is detected (e.g; more than 3 SD from the mean), the accuracy of the entry of the data point(s) will be verified (when possible) and corrected if appropriate.

Potential outliers will be identified prior to any statistical analysis. The effect of the any outliers on the analysis will determined by the statistician. Outliers will be included in or excluded from the statistical analyses as appropriate.

6.1.5 Handling of missing and/or incomplete data

Patients will be missing specific data points for a variety of reasons. With the exception of validated instruments, missing values for a given time point will not be imputed and analyses will be conducted using an observed case approach. For validated instruments, missing items will be handled according to instructions from the relevant scoring manuals.

Where both date and time are collected, partial times (i.e. times with missing minutes or times with missing hours and minutes) will be estimated by a worst-case imputation approach (e.g., impute such that duration is the longest possible value). Analyses will be conducted using an observed case approach for partial or missing dates.

